99 The primary objective of this study is to evaluate the efficacy of liraglutide 3.0 mg sc injection (in 100 combination with a reduced calorie diet and increased physical activity) compared with placebo for 101 reducing body weight in obese or overweight adults with stable BP, as measured by percent change in 102 body weight.

103

104 Secondary Objectives:

105 Secondary objectives are:

105	Secondary objectives	
106	- To ev	aluate the efficacy of liraglutide 3.0 mg sc injection as measured by:
107	-	Proportion of participants who have $a \ge 5\%$ loss in body weight
108	-	Body weight (kg)
109	-	BMI
110	-	Waist circumference
111	-	Fasting lipids
112	-	Fasting glucose
113	-	HgA1 _c levels
114	-	Three-Factor Eating Questionnaire (TFEQ) (54)
115	-	Binge Eating Scale (BES) (55)
116	- To ev	aluate the safety and tolerability of liraglutide 3.0 mg sc injection, using:
117	-	Mental status examinations
118	-	Young Mania Rating Scale (YMRS) (56)
119	-	Montgomery Asberg Depression Rating Scale (MADRS) (57)
120	-	Clinical Global Impressive Scale for modified Bipolar Disorder (CGI-BP) (58)
121	-	Physical examinations
122	-	Vital signs
123	-	12-lead electrocardiograms (ECG)
124	-	Clinical laboratory tests
125	-	Adverse event reports
126	-	Columbia-Suicide Severity Rating Scale (C-SSRS) (59)
127		
128	RESEARCH DESIG	GN AND METHODS
129		
130	Study hypothesis (es	s):
131		question is whether liraglutide 3.0 mg sc injection is efficacious for reducing body
132		verweight patients with BP. We hypothesize that liraglutide 3.0 mg sc injection will
133		e, and well tolerated treatment for weight loss in obese or overweight patients with
134		et that liraglutide 3.0 mg sc injection will display greater efficacy as compared to 135
	1 1 1 1 1	

- placebo in decreasing body weight in patients with BP who are overweight or obese without increasing
- 136 psychiatric adverse events. We also predict that liraglutide 3.0 mg sc injection will produce a greater

- percentage of patients who lose \geq 5% of baseline body weight, and improve BMI, waist circumference, 137
- fasting lipid and glucose levels, HgA1c levels, and measures of eating psychopathology. 138
- 139

140 **Endpoints:**

- The primary endpoint will be the percent change in body weight from Baseline (Week 0) to week 141
- 40/Early Termination (ET) (see Table 1 for a schedule of assessments). Secondary endpoints will include 142

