The power analysis for this study uses a two-sample t-test on the mean weight change from baseline to 510 week 40 (or endpoint for patients who discontinue prematurely) in the two treatment groups in the

- 511
- modified intent-to-treatment (ITT) sample. This sample will consist of all study participants who: 1) were 512 randomized, 2) received at least one study medication dosage, and 3) had at least one post-baseline 513
- efficacy assessment. We expect a 5% attrition rate from baseline to week 1. We therefore expect the
- 514 proposed sample size of 60 to give an ITT sample of 56. Using this ITT sample size, along with a
- 515 significance level of 0.05 and power of 0.80, we will be able to detect effect sizes as small as 0.76. 516
- 517
- This effect size corresponds to a 4.5 kg greater weight reduction in the liraglutide group vs. the placebo 518
- group. The 4.5 kg reduction was calculated (0.76 x 6.0) using an expected standard deviation (SD) of 6.0 519
- kg based on Wadden et al. (SD=7.0 at 56 weeks) and Astrup et al. (SD=5.6 for power analysis). This is a 520
- clinically meaningful difference, especially in this population, where many patients are taking 521
- 522 antipsychotics, which are associated with weight gain. We expect our primary analysis (longitudinal
- mixed model) to have more power due to the repeated visit data for each subject (60 subjects x 16 524 523
- treatment period visits = 960 maximum number of observations).

525 526

- **Statistical Methods** Chi-square, Fisher's Exact, Wilcoxon rank sum or two-sample t-tests will be used to examine statistical 527
- differences between the placebo and drug condition on baseline characteristics and categorical outcome 528
- measures. The primary analyses will be longitudinal data analyses (LDA) using PROC MIXED (SAS, 529
- Cary N.C. U.S.A.). LDA will model the mean change in the primary and secondary outcome measures, 530 over the treatment period, between the placebo and drug condition. LDA is advantageous because it 532
- 531 accounts for change over time, includes all data points, and adjusts for the correlation resulting from 533 repeated measures. These LDA models will include variables for treatment, time, and treatment x time

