Randomization will be conducted by [name], the program manager for the Lindner Center of HOPE 551 Research Institute using the program: http://www.randomization.com. Block randomization (with block 552 size of six subjects) will be used to insure relatively equal patients in both the drug and placebo groups. 553 Antipsychotic medications used to treat BP are associated with weight gain and development of obesity 554 (much more so than mood stabilizers). Randomization of subjects will therefore include current 555 antipsychotic use (receiving at least one of the following: asenapine, aripiprazole, cariprazine, 556 chlorpromazine, clozapine, haloperidol, loxapine, olanzapine, paliperidone, perphenazine, quetiapine, 557 resperidone, thiothixene, trifluoperazine, or ziprasidone) as a stratifying factor. Of note, the average 558 number of medications BP patients receive is three. We expect that nearly all patients will be receiving a 559 mood stabilizer and that about 50%-66% of patients will also be receiving an antipsychotic drug. 560 Intermittent missing visits will be treated as missing at random and no special adjustment will be used. 561 The safety population will include all randomized participants with at least one post-baseline safety 562 assessment. Statistical analyses will be conducted by [name], MS. All analyses will be conducted 563 using SAS version 9.4 (Cary, N.C., U.S.A.). Hypotheses testing will be two-sided with a significance 565 564 level of $p \le 0.05$.

566

The randomization should balance all demographic and clinical characteristic variables between the two treatment groups and generally no covariates will be used in the analyses. However, if a significant baseline difference exists between treatment groups on a demographic or clinical characteristic variable, this variable will be checked for significant correlations with the outcomes of interest. If a correlation exists, then the variable will be added as a covariate to the efficacy analysis.

572 573

574 **DATA HANDLING AND RECORD KEEPING:**

All data will be compiled using case report forms (CRFs) that will be specifically designed for this
study. Trained research coordinators will complete the CRFs. Data from CRFs will be entered and stored
in electronic and secured databases at the LCOH.

578579 ETHICS:

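### Does stating power for a t-test in kilograms, with extra power credited to 960 repeated observations, undermine the sample size for the percent-change primary endpoint?

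*Combined protocol and SAP*

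**What the plan says.** The Sample Size Calculation states that "The power analysis for this study uses a two-sample t-test on the mean weight change from baseline to" week 40 in a modified ITT sample. Participants who stop early are covered explicitly: the comparison is at "week 40 (or endpoint for patients who discontinue prematurely", so their last value counts. Sixty are randomized, 5% are expected to be lost before week 1, and 56 are expected in the analysis. With a "significance level of 0.05 and power of 0.80, we will be able to detect effect sizes as small as 0.76". The Statistical Methods section adds: "Hypotheses testing will be two-sided with a significance" level of 0.05.

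The translation to kilograms follows: "The 4.5 kg reduction was calculated (0.76 x 6.0) using an expected standard deviation (SD) of 6.0" kg. The two sources for that SD are given as 7.0 at 56 weeks and 5.6, the latter labelled as a power-analysis value. The section then expects the primary analysis (longitudinal "mixed model) to have more power due to the repeated visit data for each subject (60 subjects x 16" treatment visits, at most 960 observations) to do better than the t-test.

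The Endpoints section says: "The primary endpoint will be the percent change in body weight from Baseline (Week 0) to week" 40 or early termination. Weight in kilograms is a secondary endpoint. For the primary outcome, Statistical Methods fits a mixed model to post-baseline data only, with random intercept and slope, and reports the treatment difference at week 40. The same section names the treatment-by-time interaction as the general test of treatment effect.

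**The concern.** Four features invite doubt.

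- **Endpoint.** The power statement is in kilograms and the primary endpoint is in percent. No SD, target difference or expected baseline weight is given from which a percent-scale figure could be built. As an illustration, 4.5 kg is 5.0% of 90 kg but 3.75% of 120 kg.
- **SD.** The chosen 6.0 kg is below 7.0, the only cited value tied to a follow-up time, and below the midpoint of the two, (5.6 + 7.0)/2 = 6.3.
- **Attrition.** The only loss figure covers the first week of a 40-week trial, and the Withdrawal Criteria list several mandatory reasons to discontinue.
- **960 observations.** Sixteen correlated weights per person are not sixteen independent ones, and no within-person correlation or calculation supports the claimed gain.

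If all this were material, the 80% and the 4.5 kg would not describe the primary analysis, and a null result might be over-read as excluding a 4.5 kg effect.

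**Working it through.** **1. The plan's own figure.** Inputs from the Sample Size Calculation and Statistical Methods: 28 per arm (56 split 1:1), two-sided alpha 0.05, power 0.80. For a two-sample t-test, power comes from the noncentral t distribution with 54 degrees of freedom and noncentrality d × √(28/2). Solving for 80% gives d = 0.762. At d = 0.76 power is 79.8%. A one-sided test would have given 0.673, so the stated two-sided test is the one used. Rounding explains the rest: 60 × 0.95 = 57, taken as 56, and 0.76 × 6.0 = 4.56, written as 4.5.

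**2. Percent against kilograms.** The noncentrality depends only on the ratio of difference to SD. A t-test on percent change with 28 per arm therefore also detects 0.76 SD. If the percent-change SD were 5, 6 or 7 points (assumed; the documents give none), the detectable differences would be 0.76 × 5 = 3.8, 0.76 × 6 = 4.56 and 0.76 × 7 = 5.32 points.

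**3. Choice of SD.** At 28 per arm (noncentral t):

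| SD (kg) | Detectable difference, 0.762 × SD (kg) | Power for 4.5 kg |
|---|---|---|
| 5.6 | 4.27 | 84.0% |
| 6.0 | 4.57 | 78.7% |
| 6.3 | 4.80 | 74.7% |
| 7.0 | 5.34 | 65.6% |

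The choice matters for the kilogram reading. It does not affect the 0.76, and the plan starts from 60 participants and derives the detectable effect, not the other way round. The 7.0 comes from 56 weeks, longer than this trial's 40, so it is a sensitivity value and not shown to be the right one.

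**4. Attrition.** The 5% covers people who never enter the modified ITT sample. Later leavers remain in the 56 through their endpoint value, so the count is consistent with the test described. What is not allowed for is dilution. If 20, 30 or 40% stopped with half the effect (assumed), the mean difference would be 4.56 × (1 − 0.5 × share) = 4.10, 3.88 or 3.65 kg, and power at SD 6.0 would be 71.0, 66.1 or 60.8%. That matters only if 4.5 kg is read as the effect in those who stay on treatment. The plan defines it over the whole sample, early leavers included.

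**5. Repeated visits.** Take a true difference of 4.5 kg and a week-40 SD of 6.0 kg. With the normal approximation, power is Φ(0.75 × √14 / r − 1.96), where r is the standard error of the model's week-40 contrast relative to the t-test. The reference, r = 1, gives 80.1%.

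- Complete data, unstructured means and covariance: r = 1 exactly, so 80.1% and no gain.
- Complete data, planned linear random-coefficient model, four assumed covariance patterns (correlation between weeks 36 and 40 of 0.81 to 0.90): r = 0.997, 0.990, 0.963 and 0.940, giving 80.4, 80.9, 83.0 and 84.7%.
- Assumed dropout of 20 to 40%: linear model 74 to 84%, unstructured model 69 to 78%, completers-only t-test 71 down to 59%.

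A second check at 4.56 kg (reference 81.2%), with other assumed covariances and a linear effect, gave 81.9 to 84.2% with complete data and 75.5 to 81.2% with 20 to 40% dropout. Testing the slope difference itself gave 75.5 to 92.7%.

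**The case for a change.** The strongest case for a change is that a power statement should be made on the primary endpoint's scale and for the primary test. Here neither the week-40 contrast nor the interaction is powered as such, and the only quantity called clinically meaningful is in kilograms. The remark about extra power is offered as reassurance with nothing behind it. The gain depends on the linear trend holding: with an effect that plateaus early (assumed), the slope test fell to 67 to 77% in four covariance patterns. With dropout, week-40 power is usually below the 80.1% reference. A rewrite would cost only some wording.

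Part of this stands. The percent-scale inputs are absent, and the 960 count supports nothing by itself. It is also fair that the interaction and the week-40 difference are both named, but that is a matter for the analysis specification and not an error in the power figure.

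The rest does not carry the point. The claim of more power is possible under the planned model, so it is unquantified and not false. Any firm replacement would need a percent SD, a dropout rate and a within-person covariance that the documents do not contain. A null result should be judged by its confidence interval, whose width comes from the observed data and not from the planning SD.

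**Conclusion.** No change to the plan follows. The stated power reproduces (0.762 against 0.76; 79.8% against 80%), the standardized effect carries over to percent change, the SD is a judgement within the cited range, and early leavers are counted. Read in kilograms, the detectable difference runs from about 4.3 kg at SD 5.6 to 5.3 kg at SD 7.0, and a reader can derive this from the paragraph itself. The extra power is unproven: 0.3 to 4.6 points for the linear model with complete data, none for an unstructured one, and with 20 to 40% dropout usually a figure below the reference. These ranges rest on assumed covariances, assumed dropout and, for the linear model, a straight-line trend.

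The remaining gap is one of reporting. Closing it would correct no wrong number and would leave the 60 participants, the mixed model and the trial's conclusions as they are.

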- interaction. The statistical test for the interaction term will be the measure of a treatment effect. The 535 534 interaction term will test if the slopes of the regression lines for the liraglutide and placebo groups are 536 different. A group difference (Drug [week 40-week 0] – Placebo [week 40-week 0]) will be reported 537 which corresponds to the interaction term. For the primary outcome of percent change in body weight,
- only post-baseline data will be used in the LDA model and the difference between treatments at week 40 538
- will be reported. These mixed models will allow for random coefficients (intercept and time variable), as 539
- 540 well as an appropriate correlation structure for the error terms to account for within-subject
- correlation. The best model will be chosen using the Akaike Information Criterion-corrected 541
- (AICc). The distribution of the outcome measures will be checked for normality, and transformations will 542 be used when necessary. Also, a transformation on the time variable will be considered to optimize the 544 543
- assumed linear relationship.
- 545

- 546 Additionally, secondary endpoint analyses will be performed on all outcome measures. Using the last
- 547 observation carried forward (LOCF), baseline to endpoint change scores will be computed for each 548 measure and two-sample t-tests or Wilcoxon rank sum tests will be used to compare these changes 549 between the treatment groups.
- 550

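### Continuous secondary outcomes are compared as change from baseline without using the outcome's own baseline value, which loses precision by an amount that depends on an unstated correlation

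*Combined protocol and SAP*

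**What the plan says.** All of this is under Statistical Considerations.

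- **Longitudinal data analysis (LDA).** Statistical Methods applies it to the primary and secondary outcome measures: "These LDA models will include variables for treatment, time, and treatment x time" interaction. The interaction is the test and is described as a comparison of regression slopes. The reported effect is the week-40 minus week-0 change on drug, less the same change on placebo. Only percent weight change is restricted to post-baseline data, so for the other outcomes week 0 is one of the responses.
- **LOCF analysis.** On all outcome measures, baseline-to-endpoint change is computed for each "measure and two-sample t-tests or Wilcoxon rank sum tests will be used to compare these changes" between arms.
- **Covariates.** The default is that "generally no covariates will be used in the analyses". A demographic or clinical variable enters only if it differs significantly between arms at baseline and also correlates with the outcome, and then only in the efficacy analysis.
- **Sample size.** "The power analysis for this study uses a two-sample t-test on the mean weight change from baseline to" week 40. It assumes no baseline adjustment.

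Nothing prespecifies adjustment for an outcome's own baseline or a common baseline mean. No baseline to follow-up correlation is given for any outcome.

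**The concern.** Randomisation makes the true week-0 means equal in the two arms. A model with a treatment main effect ignores that and estimates two baseline means. A raw change score carries the full noise of the baseline reading. If one arm starts worse by chance, regression to the mean makes its change look better.

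The conditional covariate rule seldom helps. Under randomisation, a given baseline variable passes the first significance test about 5% of the time, and the rule does not reach safety analyses.

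At stake are the comparisons that the trial was not sized for: lipids, glucose, HbA1c, the Three-Factor Eating Questionnaire (TFEQ), the Binge Eating Scale (BES) and, so far as they are analysed as changes, the mood scales. About 56 participants are expected to contribute.

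**Working it through.** **1. The plan's own figure.** The inputs are "We expect a 5% attrition rate from baseline to week 1", "proposed sample size of 60 to give an ITT sample of 56" (28 per arm at 1:1), and "significance level of 0.05 and power of 0.80, we will be able to detect effect sizes as small as 0.76". A two-sided two-sample t-test with 28 per arm gives a detectable effect of 0.762, and power at 0.76 is 79.8%. Also 0.76 × 6.0 = 4.56 kg, stated as 4.5. (60 × 0.95 = 57, stated as 56.) The stated figure reproduces.

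**2. Change-score t-test.** Let r be the baseline to week-40 correlation (assumed), with equal SD s at both times. Per-person variance is 2s²(1 − r) for the change score and s²(1 − r²) after baseline adjustment. The ratio is (1 − r²) / [2(1 − r)] = (1 + r)/2, so the loss is (1 − r)/2.

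| r | Variance ratio | Loss, variance scale | Loss, SE scale | Unadjusted 56 is worth an adjusted | 60% power becomes | Detectable effect 0.76 becomes |
|---|---|---|---|---|---|---|
| 0.3 | 0.65 | 35% | 19% | 36 | 78% | 0.61 |
| 0.5 | 0.75 | 25% | 13% | 42 | 72% | 0.66 |
| 0.7 | 0.85 | 15% | 8% | 48 | 67% | 0.70 |
| 0.9 | 0.95 | 5% | 3% | 53 | 62% | 0.74 |

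Estimating one covariate at N = 56 multiplies the adjusted variance by about 1 + 1/(56 − 4) = 1.019. The net loss is then about 34% at r = 0.3 (1 − 0.65 × 1.019) and 13% at r = 0.7. The formula is for the t-test; I did not compute an equivalent for the Wilcoxon test.

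**3. Straight-line LDA.** The variance of the treatment × time term is the last diagonal element of [Σ 28 X′V⁻¹X]⁻¹, summed over the two arms. It was computed with and without the treatment main effect in X, for complete data, the visit weeks in Table 1, and V with a random intercept only. Loss on the variance scale from leaving week-0 means free:

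| Outcomes | Visits | r = 0.3 | r = 0.5 | r = 0.7 |
|---|---|---|---|---|
| Laboratory (screening taken as week 0; weeks 8, 16, 40) | 4 | 30% | 19% | 10% |
| TFEQ, BES (weeks 0 to 40) | 11 | 30% | 17% | 9% |
| Measured at every visit, 0 to 16 | 17 | 15% | 8% | 3% |

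The plan also allows random slopes. With slopes uncorrelated with intercepts, and slope variance over 40 weeks equal to 0.3 of baseline variance, the losses fall to 24/14/6%, 21/10/4% and 9/4/1%. With a negative intercept–slope correlation they can rise instead; across all the random-slope settings tried, the range was about 0.3% to 36%. With categorical time in place of a straight line, the ratio returns to (1 + r)/2.

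**4. Chance imbalance.** One standard error of the baseline difference is √(2/28) = 0.27 SD. At r = 0.5, an imbalance of that size moves the change-score result by (1 − 0.5) × 0.27 = 0.13 SD. The standard error of the change-score contrast is √[2(1 − 0.5)] × 0.27 = 0.27 SD, so the shift is half a standard error.

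**5. Does a common intercept do harm?** Suppose the arms separate linearly to week 16 and then stay apart by a constant amount, with r = 0.5. A straight line through a common intercept overstates the week-40 difference by about 2% to 10%, depending on the visit schedule. The free-intercept line is also wrong, by −11% to +5%. The error comes from the straight line, not from sharing the week-0 mean.

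**The case against.** The strongest case against is about size and scope.

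- **15–35% is not a property of the LDA.** A reader might apply it to every secondary and safety outcome. It belongs to the two-time-point change-score t-tests at r between 0.3 and 0.7. The slope contrast uses every visit, so one noisy baseline reading does not enter at full weight. With 17 visits and a random intercept the loss is 3–15%. This objection stands.
- **Every figure rests on an assumed r.** This stands; only the formula is free of that assumption.
- **Safety coverage is inferred.** A reader might take it that YMRS, MADRS and CGI-BP severity will be analysed this way. No safety model is written, and Endpoints lists these scales as safety endpoints. They come in only because safety is a secondary objective and the LOCF analysis covers all outcome measures. This stands.
- **Some outcomes fall outside the point.** CGI-BP improvement is itself a rating of change, and the ≥5% responder proportion is not a change score. For weight in kg, BMI and waist the gain is small if r is about 0.9. This stands.
- **The remedy is not free.** Dropping the main effect while keeping straight-line time can distort the week-40 estimate (step 5), and ANCOVA spends one parameter. This stands, and it shapes the fix.
- **Only secondary and exploratory comparisons are touched.** This is true. It bears on priority, not on whether the more precise analysis should be specified when the data are already collected.

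**Conclusion.** The point holds as a loss of efficiency. For continuous outcomes other than percent weight change, the planned comparisons almost never use the outcome's own baseline. They are less precise than they could be and are exposed to chance imbalance.

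In the change-score t-tests the loss is (1 − r)/2. In the straight-line LDA with a random intercept, for r from 0.7 down to 0.3, it is roughly 10–30% for laboratory outcomes, 9–30% for TFEQ and BES, and 3–15% for outcomes measured at all 17 visits. Random slopes lower these figures if uncorrelated with intercepts but need not otherwise. All figures assume complete data and 28 per arm; the change-score formula also assumes equal SDs at baseline and week 40.

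A reader might infer that the treatment estimates are biased, or that the primary result is compromised. The documents support neither. The estimates' sensitivity to baseline imbalance averages out over randomisation, percent weight change is modelled separately on post-baseline data, and the sample size and type I error are unaffected.

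**What to change.** Amend Statistical Methods, before unblinding, for each continuous outcome that has a baseline level:

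1. **Endpoint comparisons.** Replace the LOCF change-score t-test with ANCOVA on the outcome's own baseline value (the screening value for laboratory tests, which Table 1 does not repeat at Visit 0). Specify it whatever imbalance is observed, so that it does not pass through the baseline-significance rule.
2. **LDA models that include week 0.** Constrain both arms to one week-0 mean. Make time categorical, or flexible enough that early separation is not forced into a straight line, and report the week-40 contrast.
3. **Scope.** Exclude CGI-BP improvement and the ≥5% responder proportion. State whether YMRS, MADRS and CGI-BP severity are analysed as changes; if so, apply the same rule to them.

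The cost is SAP wording, about 2% of precision for one estimated covariate at N = 56, and a few extra time parameters. The baseline values are already collected, and sample size and visits do not change.

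### For percent weight change the plan names a slope test but reports a week-40 difference, and does not tie the primary p-value to that difference

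*Combined protocol and SAP*

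**What the plan says.** All references are to the combined protocol and SAP.

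- **Statistical Methods, general rule.** Longitudinal mixed models, with terms for treatment, time and their interaction, serve the primary and the secondary outcomes. The test is named: "The statistical test for the interaction term will be the measure of a treatment effect". It is explained as a comparison of the slopes of the two regression lines.
- **Statistical Methods, estimate and exception.** The between-arm difference in change from week 0 to week 40 is to be reported, a quantity "which corresponds to the interaction term. For the primary outcome of percent change in body weight" the section then sets a separate rule: "only post-baseline data will be used in the LDA model and the difference between treatments at week 40" is what will be reported. That sentence names no test.
- **Statistical Methods, model choice.** "The best model will be chosen using the Akaike Information Criterion-corrected". In addition, "a transformation on the time variable will be considered to optimize the" linear fit.
- **Endpoints.** "The primary endpoint will be the percent change in body weight from Baseline (Week 0) to week" 40 or early termination.
- **Sample Size Calculation.** Power is for a two-sample t-test on mean weight change from baseline to "week 40 (or endpoint for patients who discontinue prematurely) in the two treatment groups in the" modified intent-to-treat sample.

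**The concern.** The general rule is coherent when week 0 is in the model: the difference in change from week 0 to week 40 is then the interaction coefficient multiplied by the time elapsed, so test and estimate agree. The primary outcome breaks this link. Percent change is zero for everyone at week 0, so the plan sensibly drops that visit, but the week-40 difference then also contains the treatment coefficient.

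Read as written, the primary p-value would come from a slope comparison and would sit beside a week-40 difference that it does not test. The endpoint and the sample size both concern how much weight has changed by the end of treatment, not the rate at which the arms diverge. If most of the effect arrives early and then holds, the slope test can be non-significant when the week-40 difference is clear. If the effect grows steadily, the slope test can be significant when the week-40 difference is not.

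**Working it through.** **1. The plan's own figure.** Inputs from Sample Size Calculation: 56 analysed (28 per arm), two-sided 0.05, power 0.80. The noncentral t distribution gives a detectable effect size of 0.762, which agrees with the stated 0.76. Then 0.76 × 6.0 = 4.56, stated as 4.5 kg. This calculation concerns a change at end of treatment. No slope enters it.

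**2. The algebra.** Let D = 1 for liraglutide and x(t) be the time scale. The model mean is a + b_trt·D + c·x(t) + b_int·D·x(t).

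- With week 0 included: [difference at week 40] − [difference at week 0] = b_int·(x(40) − x(0)). This is the interaction, rescaled.
- With post-baseline data only: difference at week 40 = b_trt + x(40)·b_int.

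On untransformed time the two agree only if b_trt = 0, that is, if the fitted lines meet at week 0. The model does not impose that.

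**3. Illustration.** From the documents: 28 per arm and the 16 post-baseline visits in Table 1 (weeks 1, 2, 3, 4, 6, 8, 10, 12, 14, 16, 20, 24, 28, 32, 36, 40). Assumed, because the documents do not give them: true week-40 difference 4.56 percentage points and SD 6 (the plan's values are in kg), residual SD 1, random-intercept SD 1 or 3, a random slope making up the rest of the week-40 variance, complete data, untransformed time, t-test with 54 df.

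The visit weeks have mean 16 and sum of squares about the mean 2,410.

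- SE of 40 × slope difference = √[(2/28)·(36 − s² − 1 + 1600/2410)], where s is the intercept SD. For s = 1: √[(2/28)·34.664] = 1.574. For s = 3: √[(2/28)·26.664] = 1.380.
- SE of the model's week-40 difference = √[(2/28)·(35 + 1/16 + 24²/2410)] = √[(2/28)·35.302] = 1.588.
- SE of the observed week-40 mean difference = 6·√(2/28) = 1.604.

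The plateau curve is 4.56·(1 − e^(−t/6))/(1 − e^(−40/6)). A straight line fitted to it at these visits has b_trt = 2.13 and 40·b_int = 3.32, so the fitted week-40 difference is 2.13 + 3.32 = 5.45.

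| True effect | Quantity tested | Expected value | Ratio to SE | Power |
|---|---|---|---|---|
| Plateau | slope × 40 | 3.32 | 2.11 (s = 1), 2.41 (s = 3) | 0.55, 0.66 |
| Plateau | model week-40 difference | 5.45 | 3.43 | 0.92 |
| Plateau | observed week-40 t-test | 4.56 | 2.84 | 0.80 |
| Linear | slope × 40 | 4.56 | 2.90 (s = 1), 3.30 (s = 3) | 0.81, 0.90 |
| Linear | model week-40 difference | 4.56 | 2.87 | 0.81 |
| Linear | observed week-40 t-test | 4.56 | 2.84 | 0.80 |

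A simulation of the plateau case with s = 1 gave 0.54 for the slope test and 0.92 for the model's week-40 difference.

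**4. Which comparison is fair.** The 0.92 is not a clean gain. The fitted week-40 value, 5.45, exceeds the true 4.56 by a factor of 5.45/4.56 = 1.20, because a straight line overshoots a plateau. The fair comparator for the slope test is therefore the unbiased week-40 comparison at 0.80.

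**The case against.** **A test is named.** The interaction sentence covers every longitudinal model, so a reader who infers that the plan has no primary test goes too far. This objection stands. The defect is narrower: the named test and the reported primary estimate do not match, and the plan does not say that one replaces the other. The exception can fairly be read as a replacement, but it speaks only of reporting.

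**The plan allows for curvature.** A time transformation may be considered, and it would reduce the loss. With square-root time and the random slope on that scale, the same plateau gives x(40)·b_int = 4.42 against SEs of 1.58 and 1.39, hence slope power of about 0.79 and 0.88. This stands as a limit on the size. It does not close the gap: the fitted week-40 difference is then 0.91 + 4.42 = 5.33, still a different quantity from the interaction. It also makes the test depend on a scale not fixed in advance. One might infer that AICc selects the scale, but the text does not tie the two together.

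**Disagreement rates mix two problems.** In the plateau simulation with intercept SD 1 on untransformed time, the slope test and the model's week-40 test disagreed on significance in 0.38 of trials. Against the observed week-40 t-test the figure fell to 0.26. Part of the larger figure is therefore straight-line overshoot, a separate problem that naming the test would not cure.

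**The endpoint says week 40 or early termination.** A week-40 model contrast does not literally implement that for early leavers either. True, and a separate matter. The contrast is still a level at end of treatment, as the endpoint is, and a slope is not.

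**Conclusion.** The point holds as a mismatch between test and estimate, and should be fixed before unblinding. It follows from the wording and the algebra and needs no assumption about the data.

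Its size does depend on assumptions. With the variances assumed above, complete data and untransformed time, the slope test has power of about 0.55 to 0.66 against 0.80 when the effect levels off early (time constant 6 weeks), and 0.81 to 0.90 against 0.80 when it is linear.

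Two stronger readings are not supported. The slope test is not generally the weaker one, since under a linear effect it is equal or better. Nor do the documents provide for picking whichever result is significant. They leave the link between p-value and estimate unstated, which is not a rule for choosing. The secondary last-observation-carried-forward comparison does not settle which result is primary.

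**What to change.** State in Statistical Methods that, for percent change in body weight, the primary estimate, its 95% CI and the primary p-value all come from the week-40 treatment contrast, and that the interaction test is supportive. Fix the time scale before unblinding.

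Preferably, enter visit as a categorical factor using all 16 post-baseline visits, so that week 40 is not read off a straight line and the modified intent-to-treat sample is kept. Pre-specify a covariance structure suited to visits 1, 2 and 4 weeks apart, with a named fallback should the model fail to converge. The plan's own random intercept and slope could serve as that fallback.

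The cost is a few sentences and a contrast statement in PROC MIXED, with no new data or visits. The statistical cost is some loss of power if the effect is truly linear: in the illustration, 0.80 for an unmodelled week-40 comparison against 0.81 to 0.90 for the slope test.
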